5.1.2. Other Study Treatments

Pre- and Postinjection Medications

Prior to each SC injection of investigational product, all subjects are required to receive premedication with acetaminophen/paracetamol and an antihistamine (see [Table 5-1](#)), which will be administered at the clinic. Approximately 4 hours after the first injection, subjects will receive a second dose of acetaminophen/paracetamol.

Approximately 4 to 6 hours after subsequent injections of investigational product, subjects may take acetaminophen/paracetamol if needed (this dose may be self-administered by subjects after leaving the clinic).

Table 5-1 Pre- and Postinjection Medications

Time relative to SC injections	Medication	Dose	Route
1-2 hours before each injection	Antihistamine (cetirizine or equivalent)	10 mg ^a	Oral
1-2 hours before each injection	Acetaminophen/paracetamol	1 g	Oral
4 hours after first injection	Acetaminophen/paracetamol	1 g	Oral
4-6 hours after subsequent injections (if needed after clinic visit)	Acetaminophen/paracetamol	1 g	Oral

Abbreviation: SC=subcutaneous.

d. If an equivalent antihistamine is chosen, the dose range should be according to locally-accepted practice.

Prednisone/Prednisolone

See Section [3.1.2](#).

5.2. Treatment Assignment

Study subjects who provide informed consent and undergo Screening assessments receive a unique subject number. This assignment of subject numbers occurs at the Screening visit and serves to identify subject data in an anonymous fashion.

Subject eligibility will be established at the conclusion of the baseline evaluations (prior to randomization and first dose of investigational product at Week 0); subjects who meet all entry criteria will then be randomized in a 1:1 allocation to receive either ofatumumab SC or placebo according to a central randomization schedule.

Assignment to a treatment will be based on a computer-generated randomization list prepared by Novartis or a Novartis-approved vendor; an interactive voice response (IVR) system serves as a central system to allocate randomization numbers to each subject. The subjects and the investigative staff, except the unblinded pharmacist, will be blinded to the treatment assignment.

Subjects who withdraw from the study following informed consent, but prior to randomization to study treatment, will be classified as screen failures. In order to ensure transparent reporting of screen failure subjects, meet the Consolidated Standards of

Reporting Trials publishing requirements, and respond to queries from regulatory authorities, a minimal set of screen failure information will be collected in the electronic case report form (eCRF), including demography, screen failure details, eligibility criteria, and any serious adverse events (SAEs).

5.3. Blinding

This is a double-blind study. Each site that prepares study injections using the dilution method must designate an unblinded pharmacist (or appropriately-qualified designee) for drug preparation. All other study staff (including the investigator, subinvestigators, other site staff, the subject, and Sponsor) will be blinded to the treatment allocated to individual subjects.

In countries (including Japan) and/or study centers not using the dilution method to prepare study injections, there is no need to designate an unblinded pharmacist (or appropriately-qualified designee) for drug preparation.

The blinded study treatment assignments for individual subject will be maintained by a central IVR system. Emergency unblinding will be available via the central IVR system (refer to the SPM and IVR system guidelines for appropriate procedures to follow).

The investigator or treating physician may unblind a subject's treatment assignment **only in the case of an emergency or in the event of a serious medical condition**, when knowledge of the study treatment is essential for the appropriate clinical management or welfare of the subject, as judged by the investigator. Investigators have direct access to the subject's individual study treatment. It is preferred (but not required) that the investigator first contacts the medical monitor or appropriate study personnel to discuss options before unblinding the subject's treatment assignment. If study personnel are not contacted before the unblinding, the investigator must notify the medical monitor as soon as possible after unblinding, but without revealing the treatment assignment of the unblinded subject, unless that information is important for the safety of subjects currently in the study. The date and reason for the unblinding must be fully documented in the appropriate data collection tool.

Novartis Global Clinical Safety and Pharmacovigilance staff may unblind the treatment assignment for any subject with an SAE. If the SAE requires that an expedited regulatory report be sent to one or more regulatory agencies, a copy of the report, identifying the subject's treatment assignment, may be sent to clinical investigators in accordance with local regulations and/or Novartis policy.

If the treatment blind is broken by the site for a subject in the Treatment Period, the subject in question will be withdrawn from the Treatment Period and moved into the Follow-up Period.

During the study, investigators will not receive central laboratory data that have the potential to unblind a subject's treatment assignment. This includes lymphocytes, B-lymphocyte chemokine, [REDACTED], and human anti-human antibody (HAHA). Refer to the [REDACTED] investigator manual for additional information.

After the Week 60 visit and each Individualized Follow-up visit, the central laboratory (or designee) will provide the laboratory values and notify the investigator whether or not

a subject needs to remain in follow-up or if the subject may be discharged from the study (based on B-lymphocyte counts and IgG levels).

Sponsor unblinding for analyses will occur after all subjects have completed the Week 60 visit, been withdrawn from the treatment period, or the study has been terminated (see Section 8.3.4).

5.4. Product Accountability

In accordance with local regulatory requirements, the investigator, designated site staff, or head of the medical institution (where applicable) must document the amount of investigational product administered to study subjects, and the amount received from and returned to Novartis, when applicable. Product accountability records must be maintained throughout the course of the study.

The designated pharmacist must keep drug inventory and accountability logs. The inventory will include details of ofatumumab SC and placebo received and dispensed (administered) to subjects, batch, and identification numbers. All unused prefilled syringes (supplied by Novartis) must be kept until reconciliation of delivery records with accountability logs by the monitor. After the monitor has performed accountability, the site may destroy the syringes, unless otherwise instructed. An accounting must be made of any drug deliberately or accidentally destroyed. Discrepancies between the amount of ofatumumab SC and placebo received and dispensed must be reconciled.

** In Japan, unused investigational products will be collected at the end of the study by the Sponsor or Sponsor's consignee.*

5.5. Treatment Compliance

Investigational product will only be administered in the clinic by trained site personnel. Each dose will be recorded in the eCRF.

5.6. Concomitant Medications and Non-Drug Therapies

5.6.1. Permitted Medications and Non-Drug Therapies

Subjects may take other medications for treatment of the symptoms associated with PV, so long as they do not fall into any of the prohibited medications categories (Section 5.6.2). The appearance of 1 or 2 new lesions, not otherwise meeting the criteria for disease flare/relapse, may be treated with supportive care, such as topical preparations.

If the investigator is in any doubt about whether a concomitant medication is permitted during the study, he/she should discuss it with the medical monitor.

5.6.2. Prohibited Medications and Non-Drug Therapies

The medications and therapies/treatments listed in Table 5-2 will not be allowed during the study (including the Screening, Treatment, and Individualized Follow-up Periods).

Use of prohibited medications and therapies during the study may result in the subject being withdrawn from study treatment and potentially withdrawn from the study.

Table 5-2 Prohibited Medications and Non-Drug Therapies

Medication or Therapy	Washout Before Randomization
Lymphocyte-depleting therapies, such as: 
 • IV ofatumumab (ARZERRA) • anti-CD4, total body irradiation, bone marrow transplantation • cyclophosphamide, cladribine • alemtuzumab (Campath) • mitoxantrone 	
 • At any time • At any time • 6 months • 6 months • 6 months
Rituximab or other anti-CD20 treatments	18 months
Other monoclonal antibodies	Contact medical monitor
Immunoabsorption, plasma exchange/plasmapheresis, immunoglobulin therapy	6 months
Immunosuppressive or immunomodulatory agents, including azathioprine, cyclosporine, dapsone, mycophenolate, methotrexate, and tacrolimus	8 weeks
Received a live vaccine	6 weeks
Initiation of statin therapy	Applicable during the study only

Abbreviation: IV, intravenous.

** In Japan, alemtuzumab (Campath) and anti-CD4 treatments are not approved.*

5.6.3. Immunizations

The safety of (and ability to generate a primary or anamnestic response to) immunization with live attenuated or inactivated vaccines during ofatumumab treatment has not been studied. The response to vaccination could be impaired when B-cells are depleted.

It is recommended that the investigator review the subject’s immunization history as part of the initial screening procedure for a subject being considered for treatment with ofatumumab SC. Vaccination of the subject, in compliance with local area vaccination guidelines for the patient population being treated, is recommended prior to administration of ofatumumab SC. In particular and per local guidelines, hepatitis B vaccination should be considered for subjects at risk for infection with hepatitis B (or in areas with a high prevalence of hepatitis B). After treatment with ofatumumab SC, avoid administration of live attenuated vaccines until B-cell counts have normalized.

5.7. Treatment after the End of the Study

As the ofatumumab development program in the indication PV has been terminated, subjects completing the study will no longer be eligible to participate in the extension study (OPV117059). Subjects who were enrolled in the extension study prior to program termination may remain in the extension study until exit criteria are met. Subjects who

do not participate in the planned extension study will not receive any additional treatment after completion of this study.

The investigator is responsible for ensuring that consideration has been given to the post study care of the subject's medical condition, whether or not Novartis is providing specific post study treatment.

5.8. Treatment of Investigational Product Overdose

If an overdose does occur, there are no recommended medications or nondrug therapies for treatment. The investigator should use his/her clinical judgment in treating any overdose. If an overdose does occur, individuals should be managed with appropriate supportive therapy, as determined by the investigator in consultation with the medical monitor. If there are signs and symptoms associated with an overdose, these should be reported as an AE/SAE.

[figure not shown]

[figure not shown]

[figure not shown]
6. STUDY ASSESSMENTS AND PROCEDURES

Table 6-1 presents the schedule of assessments for the study. The investigator, or a medically qualified designee, is to conduct all study assessments. The investigator or designee must obtain written informed consent prior to performing any of the assessments. Record study information in the source documents and, where appropriate, the eCRF.

The Screening Period begins once the subject has provided written informed consent and lasts from 2 to 12 weeks prior to randomization.

If a visit cannot be scheduled on the appropriate date, the visit should be re-scheduled as close as possible to the planned date, ideally within ± 3 days.

Figure 6-1 Relative Timing of Key Activities on Ofatumumab SC Dosing Days

	1 to 2 hours predose	Dose Given	+1 hour postdose	+4 hours postdose	+4 to 6 hours postdose
First Dose	 Acetaminophen + Antihistamine	 Ofatumumab SC		 Acetaminophen	
	 Vital Signs			 Vital Signs	
					
Other Doses	 Acetaminophen + Antihistamine	 Ofatumumab SC	 Vital Signs		 Acetaminophen (self administered by subject, if needed)
	 Vital Signs				
					

Abbreviation: SC=subcutaneous.

Table 6-1 Time and Events Table

Period:	Screen	Core Study Period (60 Weeks)																					Early WD ^b			
	BL	Treatment Period (56 Weeks)																				F-up ^b				
Study Week:	-2 to -12 ^a	Day 0	2	4	6	8	10	12	14	16	18	20	22	24	28	32	36	40	44	48	52	56	60 ^b			
Clinic (C) or Phone (P) Visit:	C	C	C	C	C	C	P	C	P	C	P	C	P	C	C	C	C	C	C	C	C	C	C	C		
Informed consent	X																									
Eligibility criteria	X	X																								
Physical exam, weight, & height	X																									
Demography; PV & medical history	X																									
Smoking status	X	X												X										X	X	
Vital signs	X	X ^c		X ^c		X ^c		X ^c		X ^c		X ^c		X ^c	X ^c	X ^c	X ^c	X ^c	X ^c	X ^c	X ^c	X ^c	X ^c	X	X	
Electrocardiogram	X																							X	X	
Adverse events ^d	X	X	X	X	X	X	X	X	X	X	X	X	X	X	X	X	X	X	X	X	X	X	X	X	X	X
Concomitant medications	X	X	X	X	X	X	X	X	X	X	X	X	X	X	X	X	X	X	X	X	X	X	X	X	X	X
PV lesion mapping	X	X	X	X	X	X		X		X		X		X	X	X	X	X	X	X	X	X	X	X	X	X
Randomization		X																								
Study treatment administration ^e		XX		XX		X		X		X		X		X	X	X	X	X	X	X	X	X	X			
Document steroid dose	X	X	X	X	X	X	X	X	X	X	X	X	X	X	X	X	X	X	X	X	X	X	X	X	X	X
Steroid taper			X	X	X	X	X	X	X	X	X	X	X	X	X	X	X	X	X	X	X	X	X			
Laboratory ^f	X	X		H		H		X		H		H		X	H	H	X	H	H	X	H	H	X	X	X	X
Serum hCG (women only)	X																							X	X	
Urine hCG (women only)		X		X		X		X		X		X		X	X	X	X	X	X	X	X	X	X			
HAHA; hsCRP ^g		X						X						X			X			X	X	X	X	X	X	
IgG, IgM, IgA	X	X						X						X			X			X	X	X	X	X	X	
Pharmacodynamic markers ^g	X	X		X		X		X		X		X		X			X			X	X	X	X	X	X	

Period:	Screen	Core Study Period (60 Weeks)																						Early WD ^b	
		BL	Treatment Period (56 Weeks)																				F-up ^b		
Study Week:	-2 to -12 ^a	Day 0	2	4	6	8	10	12	14	16	18	20	22	24	28	32	36	40	44	48	52	56	60 ^b		
Clinic (C) or Phone (P) Visit:	C	C	C	C	C	C	P	C	P	C	P	C	P	C	C	C	C	C	C	C	C	C	C	C	C
Pharmacokinetic sample ^g		X		X		X		X		X		X		X			X			X		X	X	X	X
Pharmacokinetic substudy ^{g,h,i}		←See Table 6-3 for PK-PD substudy visits and sample collection time points→																							
Pharmacogenetics sample ^{g,h}		X																							
Serum banking for JC virus testing		X																							
Neurological symptom questionnaire	X	X	X	X	X	X	X	X	X	X	X	X	X	X	X	X	X	X	X	X	X	X	X	X	X

Abbreviations: [redacted]; admin=administration; [redacted]; BL=Baseline; BLC=B-lymphocyte chemokine; C=clinic visit; [redacted]; F-up=follow-up visit; HAHA=human anti-human antibody; hCG=human chorionic gonadotropin; hsCRP=high sensitivity C-reactive protein; Ig=immunoglobulin; P=phone visit; PD=pharmacodynamic; PK=pharmacokinetic; PV=pemphigus vulgaris; [redacted]; WD=withdrawal.

- a. Screening may be up to 12 weeks for disease consolidation/control and adjustment/stabilization of prednisone/prednisolone dose. Multiple visits (unscheduled) are permitted.
- b. If subject is not entering the extension study and CD19+ B cell counts and circulating IgG levels are below the lower limit of normal at Week 60 (or early withdrawal visit), the subject will transition into Individualized Follow-up (see Table 6-2). Subjects requiring additional hepatitis B virus testing will also return for follow-up visits for 6 months after the last dose.
- c. Vital signs should be taken before each injection of investigational product, at approximately 4 hours after the first dose, and at approximately 1 hour after subsequent doses.
- d. Adverse events (AEs) will be collected from the start of study treatment through the Core Study Period. Serious AEs assessed as related to study participation will be collected from the time a subject consents to participate in the study up to and including any follow-up contact.
- e. Premedication: Each dose of study treatment will be preceded by acetaminophen/paracetamol and an antihistamine (see Section 5.1.2).
Postdose observation and medication: After the first dose, subjects should stay at the clinic to be monitored for any injection-related AEs for a minimum of 4 hours, with acetaminophen/paracetamol administered again at 4 hours. After subsequent doses, it is recommended that subjects stay at the clinic for a minimum of 1 hour, with acetaminophen/paracetamol self-administered approximately 4 to 6 hours after dosing if needed.
Note: An additional 20-mg loading dose (total of two 20-mg injections) will be administered at Week 0 and Week 4.
- f. Laboratory assessments include hematology, clinical chemistry, and urinalysis. "H" indicates visits with only hematology.
At Screening and Week 60/early withdrawal only—Hepatitis B, Hepatitis C, pneumococcal antibody assay, and toxoid antibody assay.
- g. Collect sample predose on dosing days.
- h. Informed consent must be obtained before collecting samples for optional testing (ie, pharmacogenetics research and pharmacokinetic-pharmacodynamic substudy analyses).
- i. Only sites preidentified to participate in pharmacokinetic-pharmacodynamic substudy. See Table 6-3 for the schedule of visits for sample collection.

Note: Visits from Week 2 through Week 60 to be scheduled within ±3 days of the specified time point. Visits during Individualized Follow-up to be scheduled within ±7 days.

Table 6-2 Time and Events Table: Individualized Follow-up Period

	As applicable ^a								Early WD
Study Week for Core Study Completers:	72	84	96	108	120	132	144	156	
Study Week for Early Withdrawals:	+12	+24	+36	+48	+60	+72	+84	+96	
Adverse events (including SAEs and AEs of special interest) ^b	X	X	X	X	X	X	X	X	X
Concomitant medications	X	X	X	X	X	X	X	X	X
Document steroid dose	X	X	X	X	X	X	X	X	X
Neurological symptoms questionnaire (PML monitoring)	X	X	X	X	X	X	X	X	X
PV lesion mapping	X	X	X	X	X	X	X	X	X
Pregnancy testing (urine) (women) – test monthly for 12 months after the last dose of ofatumumab SC; subjects may test at home during months without a clinic visit	X	X	X	X					X
Hematology	X	X	X	X	X	X	X	X	X
Clinical chemistry	X	X	X	X	X	X	X	X	X
IgG, IgM, IgA	X	X	X	X	X	X	X	X	X
Human anti-human antibody	X								X
Pharmacodynamic markers (flow cytometry)	X	X	X	X	X	X	X	X	X
HBV DNA – if applicable, test every 12 weeks for 6 months after the last dose of ofatumumab SC	PRN	PRN							PRN

Abbreviations: AE=adverse event; ██████████; HBV=hepatitis B virus; Ig=immunoglobulin; PML=progressive multifocal leukoencephalopathy; PRN=as needed/as indicated; PV=pemphigus vulgaris; SAE=serious adverse event; SC=subcutaneous; WD=withdrawal.

- Subjects entering the Individualized Follow-up Period will continue to be monitored every 12 weeks, until CD19+ B-lymphocyte counts and IgG recover to \geq lower limit of normal (LLN) or to the subject's Baseline value (if <LLN) or if criteria for study withdrawal are met or for a maximum of 2 years after the last dose of ofatumumab SC.
- AEs (including AEs of special interest) and SAEs will be collected during the first year of the Individualized Follow-up Period. Only SAEs and AEs of special interest will be collected during the second year of the Individualized Follow-up Period. Any SAEs assessed as related to study participation will be collected from the time a subject consents to participate in the study up to and including any follow-up contact.

Note: Visits during Individualized Follow-up to be scheduled within ± 7 days.

Table 6-3 Time and Events Table: Pharmacokinetic-Pharmacodynamic Substudy

Period:	Baseline		Treatment Period (56 Weeks)																	F-up	Early WD
Visit Window:			±2 hours					±3 days													
Time Point:	Day 0 predose	Day 0 postdose	Day 1	Day 2	Day 3	Day 4	Day 7/ Week 1	Week 2	Week 4	Week 8	Week 12	Week 16	Week 20	Week 24	Week 36	Week 48	Week 52	Week 56	Week 60		
Pharmacokinetic sample ^a – regularly scheduled visits	X ^{a,b}							X	X	X	X	X	X	X	X	X	X	X	X	X	X
Pharmacokinetic sample – additional visits		X ^b	X	X	X	X	X														
Pharmacodynamic sample ^a – B-lymphocyte subset analyses	X								X	X	X	X	X	X	X	X	X	X	X	X	X
Adverse events	X	X	X	X	X	X	X	X	X	X	X	X	X	X	X	X	X	X	X	X	X

Abbreviations: F-up=follow-up visit; WD=withdrawal

a. Collect sample predose on dosing days.

b. Day 0 blood draws will occur predose and 4 hours postdose.

Note: from Day 1 through Day 7, pharmacokinetic samples should be collected at the same time of day (±2 hours) that the initial dose of investigational product was administered;

Week 2 through Week 60 visits should be scheduled within ±3 days of the specified time point.

****Refer to the full Time and Events table (Table 6-1) for the complete list of assessments to be performed at the regularly scheduled visits****

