Individualized Follow-up Period	If B-cell counts have not recovered by the Week 60 visit, subjects not entering the extension study will remain in an Individualized Follow-up Period until both the CD19+ B-cell counts and circulating IgG levels are \geq LLN or baseline levels (if $<$ LLN) or until 2 years after the last dose of investigational product (whichever comes first). Subjects who withdraw from treatment will also enter the Individualized Follow-up Period.
Screening Period	A Screening Period of 2 to 12 weeks will occur prior to randomization to allow subjects to achieve disease control using a stable oral dose of prednisone/prednisolone. Multiple visits to the clinic are permitted during this time to assess disease status and to adjust the oral prednisone/prednisolone dose.

Clinical Definitions:

Did not flare/relapse	Achieved remission on minimal steroid therapy and did not subsequently have a flare/relapse of disease by Week 60
Disease control	No new lesions for \geq 2 weeks
Disease flare/relapse	Appearance of \geq 3 new lesions within 1 month that do not heal spontaneously within 1 week, or when there is an extension (worsening) of lesions that were present at the randomization visit (Note: the appearance of 1 or 2 new lesions is not considered a flare/relapse)
Duration of remission on minimal steroid therapy	Total time (sum) of all periods of remission while on minimal steroid therapy (oral prednisone/prednisolone dose \leq 10 mg/day) up to Week 60

Eliminated use of systemic steroids	An oral prednisone/prednisolone dose of 0 mg/day for ≥ 2 weeks
Minimal steroid therapy	An oral prednisone/prednisolone dose of ≤ 10 mg/day
Remission	Absence of new or nonhealing (established) lesions for ≥ 8 weeks (Note: Subjects with existing, healing lesions may be considered in remission if other criteria are met.)
Remission on minimal steroid therapy	Absence of new or nonhealing (established) lesions while on an oral prednisone/prednisolone dose of ≤ 10 mg/day for ≥ 8 weeks
Sustained remission (SR)	The absence of new or nonhealing (established) lesions for ≥ 8 weeks that is sustained until Week 60
Time to remission off steroid therapy	Time from randomization to the time the subject initially tapered off all steroids for ≥ 8 weeks with an absence of new or nonhealing (established) lesions by Week 60

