3. INVESTIGATIONAL PLAN

Protocol waivers or exemptions are not allowed with the exception of immediate safety concerns. Therefore, adherence to the study design requirements, including those specified in the Time and Events Table (Table 6-1), are essential and required for study conduct.

Refer to Appendix 2 for any additional applicable country-specific requirements.

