After the last dose of ofatumumab SC or placebo at Week 56, subjects will be followed-up for a minimum of 4 weeks, with a visit scheduled at Week 60. As the ofatumumab development program in the indication PV has been terminated, subjects completing the study will no longer be eligible to participate in the extension study (OPV117059 [also known as COMB157J2301E1]). Subjects who were enrolled in the extension study prior to program termination may remain in the extension study until exit criteria are met. Subjects who do not participate in the planned extension study will not receive any additional treatment after completion of this study.

If B-cell counts have not recovered by the Week 60 visit, subjects not entering the extension study will remain in an Individualized Follow-up Period until both the CD19+ B-cell counts and circulating IgG levels are \geq lower limit of normal (LLN) or baseline levels (if $<LLN$) or until 2 years after the last dose of investigational product (whichever comes first) (see [Figure 3-2](#)). Individualized Follow-up visits will be scheduled every 12 weeks. Subjects who withdraw from treatment will also enter the Individualized Follow-up Period (as applicable; guidance will be provided within the ██████████ visit report, laboratory values will remain blinded).

[figure not shown]
An independent data monitoring committee (IDMC) will evaluate risks relative to benefits through review of safety and efficacy data on an ongoing basis during the study. Any case of suspected or confirmed progressive multifocal leukoencephalopathy (PML) will go through independent PML adjudication and an opinion will be provided to the Sponsor.

Figure 3-1 Study Schema

Abbreviation: SC=subcutaneous.

Figure 3-2 Study Flowchart

Abbreviations: HBV=hepatitis B virus; Ig=immunoglobulin; LLN=lower limit of normal.

Table 3-1 Study Objectives and Endpoints

Primary Objective	Co-Primary Efficacy Endpoints

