3.1.3. Follow-up Period

Subjects will be followed-up for a minimum of 4 weeks after the last dose of investigational product at the Week 56 visit. The follow-up visit will include B-cell counts and other safety, efficacy, and quality of life assessments.

If B-cell counts have not recovered by the Week 60 visit, subjects not entering the extension study (OPV117059) will remain in Individualized Follow-up until:

- CD19+ B-cell counts and circulating IgG levels are \geq LLN or baseline levels (if $<$ LLN)
- Other criteria for study withdrawal/exit are met (see Section 4.4.3)
- Two years after the last dose of investigational product (whichever comes first).

The Individualized Follow-up assessments should be scheduled approximately every 12 weeks. Subjects who withdraw from treatment will also enter the Individualized Follow-up Period.

Note: Subjects who are hepatitis B surface antigen (HBsAg) negative, hepatitis B core antibody (anti-HBc) positive, and hepatitis B virus (HBV) DNA negative (or if in Japan and HBsAg negative, anti-HBc (HBcAb) negative, but hepatitis B surface antibody [HBsAb] positive) must continue HBV DNA polymerase chain reaction (PCR) monitoring at a minimum of every 12 weeks for 6 months after the last dose of study treatment.

For subjects who participate in the extension study, OPV116910 (also known as COMB157J2301) Week 60 study assessments will be completed before any study-related assessments are performed for the extension study.

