4.4.2. Discontinuation of Investigational Product

Subjects must discontinue investigational product for any of the following reasons:

- Sponsor request, for reasons such as significant protocol deviation (and after discussion with the investigator).
- Study is terminated by the Sponsor.
- Subject meets PML discontinuation criteria (see [Appendix 4](#)).
- Subject develops any other serious opportunistic or atypical infection.
- Subject meets liver chemistry stopping criteria (see [Appendix 3](#)).
- Subject initiates treatment with a prohibited PV disease-modifying drug.
- Subject becomes pregnant.
- Subject experiences a serious or life-threatening cardiac arrhythmia.

Any subject who discontinues from the Treatment Period should complete an Early Withdrawal Visit and transition into the Individualized Follow-up Period for important safety monitoring (as applicable; see Section 3.1.3), unless he/she meets a criterion for mandatory withdrawal from the study (see Section 4.4.3).

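### Table 6-1 footnote b makes entry to Individualized Follow-up depend on low B cells and low IgG together, whereas the protocol body starts it on B-cell non-recovery alone

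*Protocol*

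**What the plan says.** **Entry, schedule.** Table 6-1 footnote b is attached to the Week 60 follow-up and early-withdrawal columns. For subjects not entering the extension study, it gives the condition as "CD19+ B cell counts and circulating IgG levels are below the lower limit of normal at Week 60 (or early withdrawal visit").

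**Entry, body text.** The definitions, the Summary and Section 3.1 say: "If B-cell counts have not recovered by the Week 60 visit, subjects not entering the extension study will remain in an Individualized Follow-up Period". Section 3.1.3 agrees: "If B-cell counts have not recovered by the Week 60 visit, subjects not entering the extension study (OPV117059) will remain in Individualized Follow-up until". None of these has an IgG condition for entry.

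**Exit.** Section 3.1 says subjects "will remain in an Individualized Follow-up Period until both the CD19+ B-cell counts and circulating IgG levels are" at LLN, or at baseline if baseline was below LLN. Otherwise follow-up ends two years after the last dose. Table 6-2 footnote a has the same two-marker recovery rule ("until CD19+ B-lymphocyte counts and IgG recover to").

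**Early withdrawals.** The definitions, the Summary and Section 3.1.3 send treatment withdrawals to follow-up with no laboratory condition. Section 4.4.2 says they "should complete an Early Withdrawal Visit and transition into the Individualized Follow-up Period for important safety monitoring"; it and Section 3.1 add that this is as applicable.

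**Who decides.** Under Section 5.3 and Table 6-5 footnote a, the central laboratory (or designee) supplies the values after Week 60 and tells the investigator whether the subject stays. Section 5.3 names B-lymphocyte counts and IgG as the basis. Neither place says how the two are combined.

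**Adverse events.** Section 6.3.7 and Table 6-1 footnote d end collection of all AEs with the Core Study Period. Table 6-2 footnote b collects all AEs through the first year of Individualized Follow-up, and only SAEs and AEs of special interest in the second.

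**The concern.** The footnote sits at the point in the schedule where the decision is made, and it is the only entry criterion in that table. Section 3 says that "adherence to the study design requirements, including those specified in the Time and Events Table (Table 6-1), are essential and required for study conduct". A site that takes the footnote as its entry criterion could release a subject who is still B-cell depleted but has normal IgG. At stake is the 12-weekly safety follow-up in Table 6-2: the PML questionnaire, AEs, hematology, immunoglobulins and flow cytometry.

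Amendment 8 closes the extension study to subjects now completing, so each remaining completer reaches this decision.

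The same footnote also covers the early-withdrawal visit. There it attaches a laboratory condition that the definitions, the Summary and Section 3.1.3 do not impose.

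**Working it through.** The main check is logical. The rules are set against the four possible states at Week 60 for a completer not entering the extension study.

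| CD19+ | IgG | Body text (definitions, Summary, 3.1, 3.1.3) | Footnote b | Exit rule met? |
|---|---|---|---|---|
| low | low | enter | condition met | no |
| low | normal | enter | condition not met | no |
| recovered | low | not triggered | condition not met | no |
| recovered | recovered | not triggered | condition not met | yes |

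Footnote b and the body text part company in one state: low CD19+ with normal IgG.

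**Missing baseline alternative.** Take a subject whose baseline values were both below LLN and who is back at baseline on both. Footnote b is met, yet the exit rule is already satisfied. The omission can therefore also pull in someone who counts as recovered.

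**Is the disputed state plausible at Week 60?** Inputs: last dose at Week 56; dosing every 4 weeks; predicted inhibition above 97.5% in 90% of subjects at steady state (Week 12) and predicted median repletion to LLN about 28 weeks after dosing stops (Section 3.3); adult CD19+ reference range 110 to 660 cells/uL (Appendix 13).

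- Time since last dose at Week 60: 60 − 56 = 4 weeks, one dosing interval.
- Count left after 97.5% inhibition from the upper reference limit: 660 × (1 − 0.975) = 16.5 cells/uL, below the LLN of 110.
- Baseline needed to remain at LLN under that inhibition: 110 / 0.025 = 4,400 cells/uL.
- Predicted median repletion: 56 + 28 = Week 84, which is 84 − 60 = 24 weeks after the Week 60 visit.

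If the Week 12 suppression holds to Week 60 under full dosing, most ofatumumab subjects have low CD19+ at Week 60. How many of them also have normal IgG is not in the documents, so no head count follows.

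**Follow-up that the body text requires.** Table 6-2 schedules completers at Weeks 72, 84, 96, 108, 120, 132, 144 and 156, a maximum of 8 visits. A subject with normal IgG who repletes at the predicted median is seen at Weeks 72 and 84, which is 2 visits.

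**AE item.** Follow-up year 1 runs to Week 60 + 52 = Week 112, so the conflicting AE instructions cover 4 completer visits: Weeks 72, 84, 96 and 108.

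**The case against.** The strongest reply is that no subject is discharged by a footnote. The central laboratory notifies the site after Week 60 and after each follow-up visit, and four consistent places in the protocol outweigh one footnote. A wrong discharge would need either a laboratory rule built on footnote b or a site acting against its notice. The documents show neither. This stands, and it limits the consequence. It does not remove the conflict, because the combining rule is not stated and sites receive the values.

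Several stronger readings are tempting but not supported:

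- *A reader might infer that footnote b orders discharge, so that IgG decides who is followed and a B-cell-depleted subject with normal IgG gets no visits.* The footnote says if, not only if. It states when a subject moves to follow-up and is silent on everyone else.
- *A reader might infer that Section 3 ranks Table 6-1 above Sections 3.1 and 3.1.3.* It requires adherence to the study design requirements, of which the table is one part. Sections 3.1 and 3.1.3 are design requirements too.
- *A reader might count the difference between footnote b and the both-must-recover exit rule as a second error.* Entry and exit criteria may differ. Section 3.1.3 itself enters on B cells and exits on B cells plus IgG.
- *A reader might add the either/or exit wording in SAP Sections 3 and 3.4.* That is background in a SAP stated to be based on Amendment 6, and the SAP only lists AEs from Individualized Follow-up.

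Figure 3-2, the study flowchart, could not be seen. It may make the intended route clearer to sites.

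The scale is also small: the SAP reports 69 randomized, and the program has been terminated.

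**Conclusion.** Footnote b is wrong as written. It conflicts with the entry rule in the definitions, the Summary and Sections 3.1 and 3.1.3 for completers with low CD19+ and normal IgG. It leaves out the baseline alternative, and it puts a laboratory condition on early withdrawals that the definitions, the Summary and Section 3.1.3 do not impose. The likely origin is in Appendix 15: the two-marker condition was the exact complement of the either/or exit rule in force before Amendment 7, and Table 6-1 is not among the places listed as updated when exit became both/and. The finding does not depend on that history, since the conflict lies within current text.

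The size is bounded but not known. Low CD19+ at Week 60 is expected in most fully dosed ofatumumab subjects, on the assumption that predicted steady-state suppression persists. The normal-IgG share is unknown, and an actual wrong discharge is possible rather than demonstrated. The matter concerns safety follow-up only; the co-primary analyses do not depend on it. It should be corrected because the rule is operative, protects subjects and is cheap to put right. The AE-collection conflict is a separate and equally plain inconsistency.

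**What to change.** 1. **Footnote b.** Reword so that a subject not going into the extension study moves to Individualized Follow-up (Table 6-2) when the Week 60 CD19+ count has not recovered to at least LLN, or to baseline where baseline was below LLN. Add that subjects withdrawing early from treatment enter under Sections 3.1.3 and 4.4.2, and remove the early-withdrawal visit from the laboratory condition.
2. **Section 5.3.** Add one sentence saying that the central laboratory applies this entry rule and the both-must-recover exit rule.
3. **Sponsor decision.** If subjects with recovered B cells but low IgG should also be followed, the entry wording in both footnote b and Section 3.1.3 should become either marker not recovered.
4. **AE collection, separately.** Align Section 6.3.7 and Table 6-1 footnote d with Table 6-2 footnote b: all AEs in follow-up year 1, then SAEs and AEs of special interest in year 2.

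A clarification letter or administrative amendment is enough. Items 1 and 2 add no visits beyond those Section 3.1.3 already requires. Item 3, if adopted, would add follow-up for subjects with recovered B cells and low IgG. Item 4 adds some non-serious AE entry at up to 4 year-1 visits per subject.
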